### **3.3.4      Removal of subjects from therapy or assessments**

#### **3.3.4.1      Removal of individual subjects**

An individual subject is to be removed from the trial if:

1. The subject withdraws consent for trial treatment or trial participation, without the need to justify the decision
2. The subject needs to take concomitant drugs that interfere with the investigational product or other trial medication
3. The subject is no longer able to participate for other medical reasons (such as surgery, adverse events (AEs), or diseases)
4. An AE or clinically significant laboratory change or abnormality occurred that the Investigator judges to warrant discontinuation of treatment. This may include cases of

sustained symptomatic hypotension or hypertension, or of clinically relevant changes in ECG requiring intervention.

5. The subject shows an elevation of AST and/or ALT  $\geq 3$ -fold ULN combined with an elevation of total bilirubin  $\geq 2$ -fold ULN (measured in the same blood sample) and/or needs to be followed up according to the 'DILI checklist' provided in the ISF.
6. The subject experiences a serious adverse event
7. For BA part only: The subject experiences a drug-related AE of severe intensity

In addition to these criteria, the physician may discontinue subjects at any time based on his or her clinical judgment.

A subject can also be removed from the trial if eligibility criteria are being violated or if the subject fails to comply with the protocol (for instance, by non-adherence to dietary rules, or non-attendance at study assessments).

If a subject is removed from or withdraws from the trial prior to first administration of trial medication, the data of this subject will not be entered in the case report form (CRF) or trial database and will not be reported in the clinical trial report (CTR). If a subject is removed from or withdraws from the trial after first administration of trial medication, this will be documented and the reason for discontinuation must be recorded in the CRF. In this case, the data will be included in the CRF/trial database and will be reported in the CTR. At the time of discontinuation a complete end of trial examination will be performed if possible and the information will be recorded in the CRFs. If the discontinuation occurs before the end of the REP (see Section [5.2.2.2](#)), the discontinued subject should if possible be questioned for AEs and concomitant therapies at or after the end of the REP in order to ascertain collection of AEs and concomitant therapies throughout the REP, if not contrary to any consent withdrawal of the subject. These discontinuations will be discussed in the CTR.

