### 6.2.2 Treatment periods

Study participants will be admitted to trial site at least 1 hour prior to administration of the trial medication. They will be kept under close medical surveillance for at least 24 hours following drug administration. Thereafter the subjects will be allowed to leave the trial site after formal assessment and confirmation of their fitness. Afterwards the study will be performed in an ambulatory fashion until the end-of-study examination.

For the SRD part, each subject will receive one dose of the respective trial medication (BI 730460 or placebo) at visit 2. The participants of the BA part will receive the respective trial medication (BI 730460) at visit 2 and 3. Details on treatments and procedures of administration are described in Section [4.1.4](#).

For details on time points and procedures for collection of plasma and urine samples for PK analysis, refer to [Flow Chart](#) and Section [5.5.2](#).

The safety measurements performed during the treatment period are specified in Section [5.2](#) of this protocol and in the Flow Chart. For details on time points for all other trial procedures, refer to the Flow Chart. AEs and concomitant therapy will be assessed continuously from screening until the end of trial examination.

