Descriptive statistics of parameters are calculated only when at least 2/3 of the individual parameter estimates of a certain parameter are available. If the actual sampling time will not be recorded or will be missing for a certain time point, the planned time will generally be used for this time point instead. Pharmacokinetic parameters which cannot be determined will be identified by "not calculated" (NC).

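### In the SRD part, an SAE, liver signal or interfering drug removes an already dosed subject from the whole trial, and no provision continues the scheduled PK samples and serial ECGs

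*Protocol*

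**What the plan says.** The list in Protocol Section 3.3.4.1 begins "An individual subject is to be removed from the trial if". Three criteria apply without further condition once met:

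- Item 2: "The subject needs to take concomitant drugs that interfere with the investigational product or other trial medication".
- Item 5: combined transaminase and bilirubin elevations, "and/or needs to be followed up according to the 'DILI checklist' provided in the ISF".
- Item 6: any serious adverse event.

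Item 4 covers AEs and laboratory changes that the investigator judges to warrant stopping treatment. Item 3 covers subjects no longer able to take part for medical reasons. Only item 7 is restricted to one part: "For BA part only: The subject experiences a drug-related AE of severe intensity".

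Section 6.2.2 sets the SRD dosing: "For the SRD part, each subject will receive one dose of the respective trial medication (BI 730460 or placebo) at visit 2".

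For a removed subject, Section 3.3.4.1 states: "At the time of discontinuation a complete end of trial examination will be performed if possible". Data already collected after dosing are kept and reported. AEs and concomitant therapies are to be asked for at or after the end of the residual effect period (REP), if possible. Section 5.2.2.2 says that the length of the REP is not known.

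**The concern.** The heading of Section 3.3.4 names therapy and assessments as two things a subject may be removed from, but the list below it has a single outcome, leaving the trial. Once an SRD subject has been dosed, that outcome cannot spare any drug. It can only cut short the observation schedule. The restriction of item 7 to the bioavailability (BA) part, where a second dose follows, shows that the criteria can be limited by part. Items 2, 5 and 6 carry no such limit.

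The missing data would then be caused by the safety event. The analyses exposed are:

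- AUC0-∞ in the dose-proportionality model (SAP Section 7.5.2);
- the time-matched concentration–QTcF pairs (SAP Section 7.8.4);
- the on-treatment ECG, vital-sign and laboratory tables.

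In a first-in-man trial with six active subjects per dose, each such subject carries weight.

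**Working it through.** The documents give no removal rate or dropout allowance, so there is no stated figure to reproduce.

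**1. What continues after removal.**

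| Element | Provision | Continues? |
|---|---|---|
| End-of-trial examination | Section 3.3.4.1; SRD Flow Chart footnotes 4 and 14 | Yes, if possible: one single ECG and one safety laboratory, no PK sample |
| Liver signal | Section 5.2.2.1, DILI checklist | Yes |
| Clinically relevant abnormal values | Section 6.2.3 | Yes, until acceptable |
| (S)AEs already present | Section 5.2.2.2 | Yes |
| New AEs | Section 3.3.4.1, to the end of the REP | No defined date, as the REP is unknown |
| Scheduled PK samples | None found | No provision |
| Serial triplicate ECGs | None found | No provision |

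SAP Table 6.7: 1 shows no central evaluation for the end-of-trial ECG, so it does not replace a lost triplicate in the central data.

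**2. Scheduled points lost.** Post-dose times from the SRD Flow Chart:

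- PK: 0.5, 1, 1.5, 2, 2.5, 3, 4, 6, 8, 10, 12, 24, 34, 48, 72, 96, 168 h = 17.
- Triplicate ECG: 0.5, 1, 2, 3, 4, 6, 8, 10, 12, 24, 34, 48 h = 12. Each coincides with a PK sample, so each lost ECG time is also a lost concentration–QTcF pair.
- Laboratory: 4, 24, 72, 168 h = 4 (the last is haematology only).

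| Removed just after | PK lost | ECG lost | Laboratory lost |
|---|---|---|---|
| 4 h | 10/17 | 7/12 | 3/4 |
| 24 h | 5/17 | 2/12 | 2/4 |
| 48 h | 3/17 | 0/12 | 2/4 |

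**3. Share of AUC0-∞ beyond the last sample.** Assume mono-exponential decline and ignore absorption: share = exp(−ln 2 × t / t½). The 14 h half-life is the anticipated value in Section 2.3. The range 20 to 27 h is that reported for the similar compound in Section 1.2.5, used here as a sensitivity assumption.

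- t = 24 h: 0.305 at 14 h; 0.435 to 0.540 at 20 to 27 h.
- t = 48 h: 0.093 at 14 h; 0.189 to 0.292 at 20 to 27 h.

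If removal comes before the 24 h sample and the last sample is at 12 h, 6 of 17 samples are lost, the share at 14 h is 0.552, and AUC0-24 is incomplete. Cmax is little affected once the first hours have passed.

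**4. The two-thirds rule.** Section 7.3.5: "Descriptive statistics of parameters are calculated only when at least 2/3 of the individual parameter estimates of a certain parameter are available". With six active subjects, 2/3 × 6 = 4 values are needed, so three missing values would suppress the summary. The probability of at least 3 of 6, binomial, at assumed rates of a missing value:

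| Assumed rate | P(at least 3 of 6) |
|---|---|
| 2% | 0.02% |
| 5% | 0.2% |
| 10% | 1.6% |
| 20% | 9.9% |

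**5. AE window.** Section 5.2.2.2 counts AEs up to the end-of-trial examination as on treatment, and Section 7.3.3 assigns later ones to post-study. After a subject's end of trial there is no active monitoring for new AEs. If the examination at removal marks that end, the on-treatment window closes then instead of at Day 9 to 13.

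**The case against.** The strongest reply is that the protocol does not abandon these subjects. The end-of-trial examination, the DILI checklist, the testing of abnormal values, the follow-up of (S)AEs and the monitoring of ECG abnormalities in Section 5.2.4.1 all remain. This stands. A reader might infer that laboratory and ECG collection simply ends, and the documents do not support that: the scheduled series ends, and follow-up of the event does not. The primary endpoint is largely protected for the same reason.

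Three further limits also stand:

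- Removal before dosing does spare the dose, and Section 3.3.4.1 provides for it. The point concerns dosed SRD subjects only.
- Items 3 and 4 depend on inability to take part or on the investigator's judgment, so not every AE forces removal. A severe drug-related but non-serious AE does not by itself do so in the SRD part.
- A reader might infer that three removals would leave a dose without descriptive AUC0-∞. That requires AUC0-∞ to be undeterminable after early removal, and the documents set no limit on extrapolation. It also requires an unlikely number of removals.

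Nor do the documents show that removals would cluster at the highest exposures: item 6 covers any SAE, related or not, on active drug or placebo. Finally, SAP Section 4 reports that all subjects up to 200 mg completed follow-up and that the BA part was not started. This limits the practical effect now, but does not make the rule sound.

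**Conclusion.** The point holds for already dosed SRD subjects who meet item 2, 5 or 6, and item 4 where the investigator so judges. They leave the whole trial when no dose remains to be withheld, and nothing continues their scheduled PK samples and serial ECGs. Per removed subject the loss is material, and for AUC0-∞ its size depends on the assumed half-life and mono-exponential decline. Across the trial the effect is likely small at low event rates, and suppression of a dose group's summary is improbable. The AE window is a secondary uncertainty, because it depends on whether the examination at removal ends the trial for that subject. This is a gap in design and wording that makes data missing because of safety events. It is not a calculation error.

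**What to change.** Reconcile Section 3.3.4.1 with Sections 5.2.2.2, 6.2.2 and 6.2.3:

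- Separate no further trial medication from no further assessments.
- State that already dosed subjects remain in the trial for the PK, ECG, laboratory and AE data collection already in the Flow Chart, to Day 9 to 13, subject to consent and the investigator's medical judgment.
- Tie the end of AE questioning to a defined visit instead of an unknown REP.
- Handle PK values affected by restricted medication or emesis under the exclusion rules already in SAP Section 6.3.

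Dosing, stopping criteria and medical management are unchanged. The cost is wording, since the visits and samples are already scheduled. The small downside is that some PK values will need an exclusion decision at the Report Planning Meeting. For this trial, with SRD follow-up complete, the remaining use is to report clearly which data any removed subject contributed, and to correct the wording in later protocols.

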#### 3.3.4.2 Discontinuation of the trial by the sponsor

Boehringer Ingelheim reserves the right to discontinue the trial overall or at a particular trial site at any time for any of the following reasons:

1. New toxicological findings or serious adverse events invalidate the earlier positive benefit-risk-assessment. Dose escalation in the SRD part or treatments in the BA part will be terminated if more than 50% of the respective subjects of one dose level or treatment group show drug-related and clinically relevant adverse events of moderate or severe intensity, or if at least one drug-related serious adverse event is reported.
2. The expected enrolment goals overall or at a particular trial site are not met
3. Violation of GCP, or the CTP by a trial site or investigator, disturbing the appropriate conduct of the trial
4. The sponsor decides to discontinue the further development of the investigational product.
5. Dose escalation in the SRD part or treatments in the BA part will be stopped if at least 2 subjects on the respective active treatment (at one dose level or in the BA part) have relevant individual QT prolongations, i.e. absolute QT or QTc greater than 500 ms, as confirmed by a repeat ECG recording, or a QTc increase of greater 60 ms from baseline

in connection with absolute QT or QTc greater than 500 ms, as confirmed by a repeat ECG recording.

6. Dose escalation will be stopped, if the  $C_{max}$  or  $AUC_{0-24}$  of at least 1 subject of one dose group increases above the following exposure thresholds or if the estimated gMean exposure is expected to exceed a  $C_{max}$  of 2,900 nM or an  $AUC_{0-24}$  of 49,000 nM\*h. Estimation will be done based on preliminary PK results of preceding dose groups (see Section [2.1](#)).
7. Occurrence of severe non-serious adverse events considered as drug-related by the investigator in 2 subjects of the same cohort (4 subjects), or 2 subjects of the same dose group (8 subjects), or 2 subjects of the BA group (12 subjects)

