2. The time is approximate; the respective procedure is to be performed and completed within 3 h prior to drug administration. Allocation to treatment may be performed at any time following enrolment but must be completed prior to (first) drug administration.
3. If several actions are indicated at the same time point, the intake of meals will be the last action.
4. End of trial examination includes physical examination, vital signs, ECG, safety laboratory, recording of AEs and concomitant therapies.
5. Only urine drug screening and alcohol breath test will be done at this time point.
6. AEs and concomitant therapies will be recorded throughout the trial, but will be specifically asked for at the time points indicated in the Flow Chart above.

7. Safety laboratory to be taken and to be medically evaluated within 3 days prior to administration of study drug; this ambulatory visit including the safety laboratory can be omitted, if the screening examination is performed on Days -3, -2 or -1.
  8. Two blood sample for stability testing will be taken at this time point (refer to Section [5.5.2.4](#))
  9. The ECG recording has to be performed as triplicate at this time point
  10. Sampling times and periods may be adapted based on information obtained during the trial (e.g. preliminary PK data) including addition of samples and visits as long as the total blood volume taken does not exceed 500 mL per subject
- 
13. Two blood samples should be collected: 4.3 mL in sodium citrate tubes and 4.5 mL in lithium heparin tubes.
  14. The ECG will be recorded as single ECG at this time point
  15. At baseline (i.e. Day 1, prior to drug administration) 3 triplicate ECGs are recorded within approximately one hour. The recordings of each first triplicate ECG should be separated by at least 15 minutes.
  16. Only haematology with automatic WBC differential (refer to Table [5.2.3: 1](#)) at this time point.

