- For safety reasons, during the single rising dose part each dose group of 8 subjects (6 on active, 2 on placebo) will be divided into two cohorts of 4 subjects each (3 on active, 1 on placebo). These two cohorts will be separated by at least 48 hours (between 1st subject of each cohort), which based on an anticipated half-life of BI 730460 of approximately 14 hours is expected to cover the period of highest risk / peak effect. The first cohort will be dosed in a single blinded, fixed sequence fashion (active - placebo - active - active) and the drug administration will be separated by at least 10 min between the first and second subject, and by at least 3 hours between the first and third subject. This design ensures that between first and second active dose of each dose level there is a time interval of at least 3 hours, which is expected to be sufficient to detect relevant acute effects of BI 730460. If BI 730460 was safe and well tolerated during these initial administrations, the remaining subjects of the respective dose level could be dosed as close as 10 minutes apart.

- A thorough ECG monitoring including continuous ECG measurement over 4 hours post dose to cover the anticipated period of highest drug exposure and additional repeated 12-lead ECGs over 48 hours following drug administration. Dose escalation would be stopped as soon as at least 2 subjects at one dose level showed relevant QT prolongation (see Section [3.3.4.2](#) for details).
- Although no clinically relevant hypotension is expected at the exposures anticipated in this trial (see Section [1.2.1](#)), nevertheless, blood pressure and heart rate will be closely monitored for potential hemodynamic effects.
- The subjects will stay at the trial site (BI Human Pharmacology Centre) for at least 24 hours after study drug administration at each dose level. Based on an anticipated half-life BI 730460 of approximately this is expected to cover the period of highest risk / peak effect.
- During in house-confinement the subjects will be under medical observation and thoroughly monitored for both expected and unexpected adverse events.
- Only if the respective dose of BI 730460 was safe and showed acceptable tolerability and if no stopping criterion was met (refer to Section 3.3.4.2), the next higher dose will be given at least 6 days later (referring to the 1st subject of each dose group).

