#### SRD part

The first part of the trial, the SRD part, is designed as single-blind, partially randomised, and placebo-controlled within parallel dose groups. Only one dose is tested within each dose group. The groups will be treated consecutively in ascending order of doses. Each group is divided into 2 cohorts of 4 subjects each (3 on active drug and 1 on placebo). On the first study day within each dose group, the first cohort will be treated in a single-blind manner in the following order: first subject (active) followed at least 10 min later by the second subject (placebo) followed at least 2 h 50 min later by the third subject (active) followed at least 10 min later by the fourth subject (active).

If BI 730460 treatment is safe and showed acceptable tolerability in the first cohort, the subjects in the second cohort will be treated not earlier than 2 days later in a single-blind

randomised manner. In the second cohort, a time interval of at least 10 min will be maintained between each administration of the trial drug to the individual subjects. A time interval of at least 6 days will be maintained between the first drug administration in the previous dose group and the first drug administration of the subsequent dose group. The decision to proceed to the next dose group will be based upon the safety, tolerability, and pharmacokinetic data of the preceding dose groups. The next dose will only be given if, in the opinion of the Investigator, no safety concerns arose in the preceding dose group (i.e. no dose-limiting events occurred) and if none of the pre-specified trial-specific stopping criteria were met (refer to Section [3.3.4.2](#)).

A documented Safety Review must take place prior to each dose escalation (see minimum data set below). Furthermore, an unscheduled safety review meeting can be requested anytime for any reasonable cause by the Principal Investigator (or an authorised deputy) or the sponsor of the study, e.g. because of any unforeseen adverse events, etc. Dose escalation will only be permitted if no safety concerns exist in the opinion of the Principal Investigator (or an authorised deputy) and the trial clinical monitor (or an authorised deputy).

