Although no formal Safety Review meeting will take place within a given dose group, safety will be continuously monitored during this trial, and an individual will only be dosed in the absence of any safety concern (i.e. no dose-limiting events occurred) and if none of the pre-specified trial-specific stopping criteria have been met (refer to Section [3.3.4.2](#)).

The minimum data set for the Safety Review consists of the following data:

- AEs in the current and preceding dose groups up to at least 48h post dosing from at least 4 subjects on active drug per dose group, including clinically relevant findings from ancillary safety testing listed below (Note: AEs may be ongoing at the time of Safety Reviews and AE information may be subject to change prior to Database Lock)
- Results from 12-lead EGG and continuous ECG monitoring in the current and preceding dose groups and from at least 4 subjects on active drug per dose group up to at least 48h post dosing.
- Vital signs in the current and preceding dose groups and from at least 4 subjects on active drug per dose group up to at least 48h post dosing.
- Clinical laboratory tests in the current and preceding dose groups and from at least 4 subjects on active drug per dose group up to at least 24h post dosing.
- Preliminary PK data for selected time as per Section [7.3.4](#).
- Check of criteria for stopping subject treatment as per Section [3.3.4.1](#)

The decision to escalate the dose will be made jointly by the Principal Investigator (or an authorised deputy) and the trial clinical monitor (or an authorised deputy) after in-depth analysis of all available safety data, especially SAEs (if occurred), AEs and out-of-range laboratory results (if considered clinically significant). Safety Reviews can be conducted face-to-face or by video/telephone conference. The trial clinical monitor is responsible for organization and minutes of the reviews. Minutes will be signed off by the Principal Investigator (or an authorised deputy) and filed in the ISF and TMF.

The investigator is allowed to alter the scheduled dose levels (e.g. add low and/or intermediate dose levels) on the basis of experience gained during the study, provided the planned and approved highest dose is not exceeded. In this case, the total number of subjects in this trial might increase. The investigator and/or the sponsor should stop dose escalation in case the safety evaluation leads to concerns that would not allow higher dosing.

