#### b) Trial site (SRD part and BA part)

All local ECGs will be evaluated by the investigator or a designee.

For the inclusion or exclusion (see Section [3.3](#)) of a subject and for the assessment of cardiac safety during the study, the QT and QTcB values generated by the computerised ECG system or their manual corrections by the investigators will be used.

In doubtful cases, ECGs may be sent upfront (i.e. prior to the regular data transfer) for cardiologic assessment by the central lab. In this case, these centrally measured results would overrule any other results obtained.

Abnormal findings, irrespective of whether they originate from central or local evaluation, will be reported as AEs (during the trial) or baseline conditions (at screening) if judged

clinically relevant by the investigator.

Any ECG abnormalities will be monitored carefully and, if necessary, the subject will be removed from the trial and will receive the appropriate medical treatment.

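### Does the 60 ms part of the QT stopping rule need rewording because it is already contained in the 500 ms part?

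*Protocol*

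**What the plan says.** Item 5 of Protocol 3.3.4.2 counts subjects with a relevant individual QT prolongation. Two or more on active treatment, at one dose level or in the bioavailability part, stop escalation or treatment. A prolongation counts if it is "absolute QT or QTc greater than 500 ms, as confirmed by a repeat ECG recording, or a QTc increase of greater 60 ms from baseline". The sentence then limits the second alternative to a rise seen "in connection with absolute QT or QTc greater than 500 ms, as confirmed by a repeat ECG recording".

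Other sections lean on this rule without restating a limit:

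- Protocol 2.3 lists it among the safety measures ("Dose escalation would be stopped as soon as at least 2 subjects at one dose level showed relevant QT prolongation") and refers back to 3.3.4.2.
- Protocol 3.1 allows the next dose only "if none of the pre-specified trial-specific stopping criteria were met".
- Protocol 5.2.4.1 b) settles which values the site uses: "for the assessment of cardiac safety during the study, the QT and QTcB values generated by the computerised ECG system", or the investigator's manual corrections of them.
- Note 15 of the single-rising-dose flow chart describes the pre-dose recordings: "At baseline (i.e. Day 1, prior to drug administration) 3 triplicate ECGs are recorded within approximately one hour".

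**The concern.** The word joining the two alternatives suggests two separate triggers, one on the absolute interval and one on the change from baseline. Because the second carries the whole of the first as a condition, only the absolute one can operate. In a first-in-man trial one would worry that a change-from-baseline criterion had been intended and then lost in drafting.

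If so, a sizeable rise that stays at or below 500 ms would never count towards the two subjects. From a baseline QTc of 400 ms, for example, a rise of up to 500 − 400 = 100 ms would not count, as long as uncorrected QT also stays at or below 500 ms. From 380 ms the figure is 120 ms. These baselines are illustrative; the protocol only excludes QTc repeatedly above 450 ms (exclusion criterion 20).

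**Working it through.** The plan attaches no power or error rate to this rule, so there is no figure to reproduce. The check is one of logic.

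**Inputs, all from Protocol 3.3.4.2 item 5**

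- A: QT or QTc above 500 ms, confirmed by a repeat ECG.
- D: QTc rise from baseline above 60 ms.
- First alternative: A. Second alternative: D and A. Rule per subject: A or (D and A).

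**Step 1. The four states of a subject**

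| A | D | Rule as written | First alternative alone |
|---|---|---|---|
| no | no | not counted | not counted |
| no | yes | not counted | not counted |
| yes | no | counted | counted |
| yes | yes | counted | counted |

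The last two columns agree in all 4 rows. Since no subject is classified differently, the count of two or more cannot differ either. Over the 4^6 = 4,096 patterns for six active subjects at a dose level, 0 differ, and the same identity covers the 12 bioavailability subjects.

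**Step 2. Does it matter what the repeat ECG confirms?** Split A and D into initial and repeat recordings, giving 2^4 = 16 patterns, and count those that meet the second alternative without the first.

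| The repeat ECG confirms | Patterns meeting only the second alternative |
|---|---|
| the value above 500 ms (plain reading) | 0 |
| both the value and the rise | 0 |
| the rise only | 1 |

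The single pattern is an initial value above 500 ms that the repeat does not confirm, with a rise above 60 ms on both recordings. This reading is strained, because the confirmation phrase follows the 500 ms condition in the same words in both alternatives. Even here a value above 500 ms is needed, so the rise still cannot trigger the rule by itself.

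**Step 3. Is there a conflict elsewhere?** Protocol 2.3 and 3.1 point back to 3.3.4.2 and give no QT limit of their own. No section sets a separate numeric stopping limit on QTc change. The sentence itself ties the rise to the absolute value. The two conditions also overlap heavily in practice: from any baseline of 440 ms or less, a QTc above 500 ms is necessarily a rise of more than 500 − 440 = 60 ms.

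**Step 4. Did the rule affect this trial?** SAP section 4 gives the reason for stopping: geometric mean Cmax at 200 mg was 1,864 nM, so the prediction at twice the dose was 2 × 1,864 = 3,728 nM, above the 2,900 nM limit. The bioavailability part was not started. SAP 7.8.4 summarises QTcF changes from baseline over time and models them against concentration, without reference to item 5.

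**The case for a change.** The strongest case for a change is that a stopping rule should say exactly what triggers it. This one names two triggers of which one is idle, and the text does not explain why the second is there. One sentence from the sponsor would settle it, at almost no cost, and would help if the wording is used again. The on-site baseline is also unnamed: Protocol 7.3.3 and SAP 6.7 define the ECG baseline for the central evaluation, which takes place after the study, while the site works from its own readings.

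The redundancy stands, and so does the gap over the on-site baseline. Neither makes the rule wrong:

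- Deleting the second alternative changes no result on the plain reading.
- Making it independent would be a new clinical criterion. Nothing in the documents shows that one was intended, and it is not for a statistical review to supply it.
- The baseline matters only if the rise acts independently, which it does not.
- The trial report can quote the rule as it stands. The documents do not show how the site applied it, so the report should not be asked to describe more than that.

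Large rises below 500 ms were also not outside review. Protocol 3.1 makes escalation a joint decision with the sponsor's clinical monitor: "Dose escalation will only be permitted if no safety concerns exist in the opinion of the Principal Investigator (or an authorised deputy". Within a dose group, the same section says that "an individual will only be dosed in the absence of any safety concern". Protocol 3.3.4.1 item 4 allows removal for relevant ECG changes, 4.1.4 lets the investigator stop dosing at any time, and 5.2.4.1 b) requires ECG abnormalities to be monitored. These safeguards rest on judgement rather than on a number, which is a fair reservation, but they apply throughout.

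**Conclusion.** The observation about the wording is correct, but it calls for no change. On the plain reading the 60 ms condition is surplus: it alters 0 of 4 subject states and hence no stopping decision. The only qualification is the strained reading, which yields 1 of 16 patterns and still requires a value above 500 ms.

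The rule can be applied as written, agrees with the sections that refer to it, and feeds no estimate or planned analysis. According to the SAP, the trial ended on exposure, with no dosing left for a reworded rule to govern.

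The conclusion rests on taking the repeat-ECG phrase to qualify the 500 ms value, as its position suggests, and on the SAP's account of why the trial stopped. It takes no position on which QT criterion is clinically appropriate.
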